Appendix 1**Criteria for Identifying Laboratory Values of Potential Clinical Relevance**

Laboratory Tests	Criteria (Normal Ranges) for Subjects 9 - 12 Years Old ^{a,b}
Chemistry	
AST	$\geq 2 \times \text{ULN}$
ALT	$\geq 2 \times \text{ULN}$
ALP	$\geq 2 \times \text{ULN}$
BUN	$\geq 24 \text{ mg/dL} (\leq 4 \text{ mg/dL} \text{ or } \geq 24 \text{ mg/dL})$
Creatinine	$\geq 0.7 \text{ mg/dL} (\leq 0.2 \text{ mg/dL} \text{ or } \geq 0.7 \text{ mg/dL})$
Uric acid	$\geq 6.7 \text{ mg/dL} (\leq 1.6 \text{ mg/dL} \text{ or } \geq 6.7 \text{ mg/dL})$
Bilirubin (total)	$\geq 1.6 \text{ mg/dL} (\leq 0.2 \text{ mg/dL} \text{ or } \geq 1.6 \text{ mg/dL})$
CPK	$\geq 2 \times \text{ULN}$
Prolactin	$\geq 21.00 \text{ ng/dL} (\leq 2.63 \text{ ng/dL} \text{ or } \geq 21.00 \text{ ng/dL})$
Hematology	
Hematocrit	$\leq 33\% (\leq 33\% \text{ or } \geq 44\%)$
Hemoglobin	$\leq 11.2 \text{ g/dL} (\leq 11.2 \text{ g/dL} \text{ or } \geq 15.5 \text{ g/dL})$
White blood count	$\leq 4.35 \times 10^3/\mu\text{L} (\leq 4.35 \times 10^3/\mu\text{L} \text{ or } \geq 13.65 \times 10^3/\mu\text{L})$
Eosinophils	$\geq 4.8\%$
Neutrophils	$\leq 40.5\% (\leq 40.5\% \text{ or } \geq 75.0\%)$
Absolute neutrophil count	$\leq 1.00 \times 10^3/\mu\text{L} \text{ or } \geq 9.00 \times 10^3/\mu\text{L}$
Platelet count	$\leq 130 \times 10^3/\mu\text{L} (\leq 130 \times 10^3/\mu\text{L} \text{ or } \geq 570 \times 10^3/\mu\text{L})$
Urinalysis	
Protein	Change from baseline
Glucose	Presence
Additional Criteria	
Chloride	$\leq 94 \text{ mEq/L} \text{ or } \geq 112 \text{ mEq/L}$
Potassium	$\leq 3.3 \text{ mEq/L} \text{ or } \geq 5.2 \text{ mEq/L}$
Sodium	$\leq 132 \text{ mEq/L} \text{ or } \geq 148 \text{ mEq/L}$
Calcium	$\leq 8.3 \text{ mg/dL} \text{ or } \geq 10.9 \text{ mg/dL}$
Glucose	
Fasting	$\geq 100 \text{ mg/dL} (\leq 70 \text{ mg/dL} \text{ or } \geq 100 \text{ mg/dL})$
Nonfasting	$\geq 139 \text{ mg/dL} (\leq 59 \text{ mg/dL} \text{ or } \geq 139 \text{ mg/dL})$
Total cholesterol, fasting	$\geq 217 \text{ mg/dL} (\leq 97 \text{ mg/dL} \text{ or } \geq 217 \text{ mg/dL})$
LDL cholesterol, fasting	$\geq 130 \text{ mg/dL}$
HDL cholesterol, fasting	$\leq 34 \text{ mg/dL} (\leq 34 \text{ mg/dL} \text{ or } \geq 75 \text{ mg/dL})$
Triglycerides, fasting	$\geq 131 \text{ mg/dL} (\leq 30 \text{ mg/dL} \text{ or } \geq 131 \text{ mg/dL})$

^aThe recommended criteria represented in this table are intended to identify on-treatment outside of normal values that could potentially be clinically relevant. Variations based on local laboratory ranges may need to be considered.

^bInformation adapted from: 1. Soghier L, Pham K, Rooney S. Reference Range Values for Pediatric Care. The American Academy of Pediatrics. 2014; 2. Hughes HK, Kahl LK. The Johns Hopkins Hospital: The Harriet Lane Handbook. 21st edition. 2015; 3. Covance central laboratory reference ranges, 2019.

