9.4.2.2 Clinical Laboratory Data

Descriptive statistics will be used to summarize the change from baseline for laboratory tests. The incidence of potentially clinically relevant laboratory tests will be summarized by time point.

Protocol 405-201-00037

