10.3 Clinical Laboratory Data

Clinical hematology, chemistry, and urinalysis are tested at screening, check-in (Day -1 or Day 1), and Day 2/ET.

For clinical laboratory tests data, baseline is defined as the last non-missing value obtained before dosing. The predose assessment will be performed either on Day -1 or

Protocol 405-201-00037

Day 1 depending on investigator's decision. If the predose assessment is missing, the baseline value will be based on the screening visit.

Clinical laboratory tests (observed and change from baseline data) will be summarized by time point and mode of administration (intact capsules or capsule contents sprinkled on a tablespoon of applesauce). The incidence of potentially clinically relevant clinical laboratory tests as defined in [Appendix 1](#) will be summarized by mode of administration. Laboratory results that are potentially clinically relevant will also be listed out by subjects.

When laboratory test is repeated, the last repeat value will be used in the summary for that visit. Unscheduled laboratory data will not be summarized in the change from baseline table but will be included in incidence table.

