Appendix 2 Criteria for Potential Clinically Significant Vital Signs

Variable	Criterion Value ^a	Change Relative to Baseline ^a
Heart rate at rest ^b	< 60 bpm or > 110 bpm	Increase or decrease of ≥ 15 bpm
Systolic blood pressure ^c		
School-age (6 to 9 years old)	< 85 mmHg or > 115 mmHg	Increase or decrease of ≥ 20 mmHg
Preadolescent (10 to 12 years old)	< 90 mmHg or > 120 mmHg	Increase or decrease of ≥ 15 mmHg
Diastolic blood pressure ^c		
School-age (6 to 9 years old)	< 50 mmHg or > 80 mmHg	Increase or decrease of ≥ 15 mmHg
Preadolescent (10 to 12 years old)	< 60 mmHg or > 80 mmHg	Increase or decrease of ≥ 15 mmHg
Orthostatic hypotension	≥ 30 mmHg decrease in systolic blood pressure and/or a decrease of ≥ 20 mmHg in diastolic blood pressure after at least 3 minutes of standing compared to the previous supine blood pressure	Not applicable (baseline status not considered)
Orthostatic tachycardia	≥ 25 bpm increase in heart rate from supine to standing	Not applicable (baseline status not considered)
Weight	Not applicable	Increase or decrease of $> 25\%$

bpm = beats per minute.

^aThe criterion value and change relative to baseline represented in this table are intended to identify on-treatment values outside of normal changes and that could potentially be clinically relevant. In order to be identified as potentially clinically relevant, the on-treatment value must meet the “Criterion Value” and also represent a change from the subject’s baseline value of at least the magnitude shown in the “Change Relative to Baseline” column. When evaluating these values, the emotional state of the subject must be taken into consideration (eg, crying, screaming) and documented as applicable.

^bInformation adapted from: Hughes HK, Kahl LK. The Johns Hopkins Hospital: The Harriet Lane Handbook. 21st edition. 2015.

^cInformation adapted from: Flynn JT, Kaelber DC, Baker-Smith CM, et al. Clinical Practice Guideline for Screening and Management of High Blood Pressure in Children and Adolescents: American Academy of Pediatrics Subcommittee on Screening and Management of High Blood Pressure in Children. Pediatrics. 2017;140(3):1-72.

Protocol 405-201-00037

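### For 27 of 28 laboratory criteria, a child beyond the limit before dosing and unchanged on Day 2 is counted in the incidence of potentially clinically relevant values

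*SAP*

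**What the plan says.** **Laboratory criteria.** SAP Appendix 1 (the same table as protocol Appendix 5) lists 28 criterion rows. All but one are fixed limits, multiples of the upper limit of normal, or simple presence. The exception is urine protein, flagged on "Change from baseline". Footnote a describes the criteria as "intended to identify on-treatment outside of normal values that could potentially be clinically relevant".

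**Laboratory incidence rule.** In SAP 10.3, "baseline is defined as the last non-missing value obtained before dosing". That baseline serves the change-from-baseline summary. The incidence of flagged values "will be summarized by mode of administration. Laboratory results that are potentially clinically relevant will also be listed out by subjects". On extra samples: "Unscheduled laboratory data will not be summarized in the change from baseline table but will be included in incidence table". Protocol 9.4.2.2 lays the table out differently: "The incidence of potentially clinically relevant laboratory tests will be summarized by time point".

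**Other safety data.** For vital signs, footnote a of SAP Appendix 2 requires the value to meet the criterion "and also represent a change from the subject’s baseline value of at least the magnitude shown" in the table. Appendix 3 has the same footnote for ECGs. The two orthostatic rows of Appendix 2 are expressly marked as not using baseline. SAP 10.2 counts adverse events that arise after dosing or worsen relative to baseline.

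**The concern.** An on-treatment incidence table is read as showing what appeared after the drug was given. Here a Day 2 value beyond the limit is counted whether it is new or was already there at check-in. With one arm and no control, the table itself offers no way to tell the two apart.

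The limits make this plausible. The Appendix 1 column is headed as criteria with normal ranges, and for BUN, uric acid, bilirubin, hematocrit, neutrophil percentage, glucose, total cholesterol, HDL and triglycerides the criterion equals one of the printed range limits. Some healthy children can be expected to lie beyond such limits. Numeric entry exclusions cover only eight tests. A child with, say, eosinophils of 5% at check-in and again on Day 2 could be eligible and would be counted.

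Mode of administration follows a capsule swallow test, not randomization. A chance difference in baseline abnormality between the two modes could therefore look like a difference between intact and sprinkled capsules.

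**Working it through.** The plan states no figure to reproduce: there is no sample-size calculation and no inference. The check is a comparison of rules, a count of rows, and an illustration.

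**1. Rules side by side.**

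| Data | Source | Baseline needed for a flag or event? |
|---|---|---|
| Adverse events | SAP 10.2 | Yes: onset after dosing, or worsening |
| Vital signs | SAP Appendix 2 | Yes, except the two orthostatic rows |
| ECG | SAP Appendix 3 | Yes |
| Laboratory | SAP Appendix 1 and 10.3 | No, except urine protein |

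**2. Row count (SAP Appendix 1).**
- Rows: 28. Less urine protein: 28 − 1 = 27 with no baseline condition.
- Tests with a numeric entry exclusion in protocol 5.2.2, item 14: platelets, hemoglobin, absolute neutrophil count, white cells, AST, ALT, CPK and creatinine, so 8. Remaining: 27 − 8 = 19.
- Less prolactin (not in protocol Table 10.2-1), with fasting and nonfasting glucose counted once: 19 − 2 = 17.
- Less ALP, whose criterion is twice the upper limit and so not at a reference limit: 17 − 1 = 16.

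**3. Weight of one child.** With 12 treated, 1/12 = 8.3 percentage points. With 6 per mode, if the split is even, 1/6 = 16.7 points.

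**4. Flags expected with no drug effect (illustration).** Among the 16 tests, 11 have a one-sided criterion, urine glucose is flagged on presence (treated here as one tail), and chloride, potassium, sodium and calcium are two-sided. Tails: 11 + 1 + 2 × 4 = 20. The share p of children beyond each tail is an assumption, because the documents give none. Expected flags at one draw in 12 children = 12 × 20 × p:
- p = 1%: 2.4
- p = 2.5%: 6.0
- p = 5%: 12.0

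This expectation does not need independence between tests. The chance that a child has at least one flag does: at p = 2.5% it is 1 − 0.975^12 × 0.95^4 = 0.40. Linked tests, such as total and LDL cholesterol, would lower it.

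**5. Part at issue.** Step 4 counts flags of any kind. Only a fraction f was also present at baseline. At p = 2.5% the carried-over flags number 6.0 × f: 1.5 at f = 0.25, 3.0 at f = 0.5, 4.5 at f = 0.75. Neither p nor f can be derived from the documents.

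**6. Predose values.** Laboratory tests are scheduled at screening, check-in and Day 2 or early termination, so only one scheduled draw is postdose. Protocol 5.2.2 calls for abnormal results to be repeated before a child is excluded, so extra predose samples are likely. SAP 10.3 has no postdose limit for unscheduled data and gives incidence by mode only. By contrast, SAP 10.4 and 10.6 split vital-sign and ECG incidence by time point as well.

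**The case against.** **The footnote already says on-treatment.** This stands. A reader might infer that the SAP directs predose unscheduled values into the incidence count. The documents do not support that: footnote a limits the criteria to on-treatment values, and SAP 10.3 treats repeats and unscheduled data in separate sentences without classing eligibility repeats as unscheduled. What remains is an ambiguity, because the section a programmer will follow does not repeat the limit.

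**Different rules for different data can be deliberate.** This stands in part. The orthostatic rows show that the SAP sometimes chooses a baseline-free flag, and the urine protein row means that laboratory incidence does not disregard baseline entirely. But the orthostatic rows state the choice and Appendix 1 does not, and an orthostatic flag already compares two positions within the child.

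**Other outputs cover the gap.** This stands in part. SAP 10.3 also gives observed and change-from-baseline summaries by time point and mode, and lists flagged results by child. With at most 12 children, a careful reader could find many of the carried-over values. The incidence table, which is the figure likely to be quoted, would still include them.

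**Eligibility removes the important cases.** This stands in part. Besides the eight numeric exclusions, protocol 5.2.1 and the note in 5.2.2 exclude clinically or medically significant laboratory abnormalities. Minor deviations remain, and those are the least consequential flags.

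**A baseline condition could hide worsening.** This stands, and is the reason for keeping children abnormal at baseline in view in a column of their own.

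**Conclusion.** The point holds as a modest improvement. For 27 of 28 criteria, a child beyond the limit at baseline and unchanged on Day 2 counts as an on-treatment finding, unlike under the adverse-event rule and most vital-sign and ECG rules. This follows from the text alone.

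Its size is 8.3 percentage points per carried-over child out of 12, or 16.7 out of 6 if the modes split evenly. A reader might take the illustrative 6 flags as the number of spurious findings. They are not: they include values newly out of range on Day 2, which would still be counted after the fix, and they rest on an assumed 2.5% per tail and on the 16 cut-offs lying near reference limits. The documents do not allow the number of carried-over children to be derived.

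The missing postdose limit is an ambiguity, and the missing time-point split is a discrepancy with protocol 9.4.2.2. The consequence is confined to descriptive safety tables. The primary pharmacokinetic endpoints are unaffected.

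**What to change.** In SAP 10.3:

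1. State that laboratory incidence counts postdose values only, scheduled or unscheduled.
2. Present incidence by baseline status, using the baseline the section already defines. The main count is children who did not meet the criterion at baseline and meet it after dosing. The denominator is children who did not meet it at baseline and have a postdose value.
3. Show children who met the criterion at baseline in a separate column, noting any worsening.
4. Restore the time-point split of protocol 9.4.2.2, or say why it is dropped. Once predose values are out, Day 2 or early termination is the only scheduled time point, so this adds little.

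The criteria in Appendix 1 need not change. The cost is slightly more programming for one table, with no new data. The downside is that worsening from an abnormal baseline appears in the separate column, not in the main count.

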Appendix 2 Criteria for Potential Clinically Significant Vital Signs

Variable	Criterion Value ^a	Change Relative to Baseline ^a
Heart rate at rest ^b	< 60 bpm or > 110 bpm	Increase or decrease of ≥ 15 bpm
Systolic blood pressure ^c		
School-age (6 to 9 years old)	< 85 mmHg or > 115 mmHg	Increase or decrease of ≥ 20 mmHg
Preadolescent (10 to 12 years old)	< 90 mmHg or > 120 mmHg	Increase or decrease of ≥ 15 mmHg
Diastolic blood pressure ^c		
School-age (6 to 9 years old)	< 50 mmHg or > 80 mmHg	Increase or decrease of ≥ 15 mmHg
Preadolescent (10 to 12 years old)	< 60 mmHg or > 80 mmHg	Increase or decrease of ≥ 15 mmHg
Orthostatic hypotension	≥ 30 mmHg decrease in systolic blood pressure and/or a decrease of ≥ 20 mmHg in diastolic blood pressure after at least 3 minutes of standing compared to the previous supine blood pressure	Not applicable (baseline status not considered)
Orthostatic tachycardia	≥ 25 bpm increase in heart rate from supine to standing	Not applicable (baseline status not considered)
Weight	Not applicable	Increase or decrease of $> 25\%$

bpm = beats per minute.

^aThe criterion value and change relative to baseline represented in this table are intended to identify on-treatment values outside of normal changes and that could potentially be clinically relevant. In order to be identified as potentially clinically relevant, the on-treatment value must meet the “Criterion Value” and also represent a change from the subject’s baseline value of at least the magnitude shown in the “Change Relative to Baseline” column. When evaluating these values, the emotional state of the subject must be taken into consideration (eg, crying, screaming) and documented as applicable.

^bInformation adapted from: Hughes HK, Kahl LK. The Johns Hopkins Hospital: The Harriet Lane Handbook. 21st edition. 2015.

^cInformation adapted from: Flynn JT, Kaelber DC, Baker-Smith CM, et al. Clinical Practice Guideline for Screening and Management of High Blood Pressure in Children and Adolescents: American Academy of Pediatrics Subcommittee on Screening and Management of High Blood Pressure in Children. Pediatrics. 2017;140(3):1-72.

Protocol 405-201-00037

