10.4 Vital Sign Data

Vital signs, including systolic and diastolic blood pressure and heart rate, will be assessed at check-in, predose (within 2 hours before dosing) on Day 1, and 3 hours postdose on Day 1.

The baseline of vital sign is defined as data collected within 2 hours before dosing on Day 1. If a parameter is missing on Day 1 then the screening data collected at check-in will be used.

Change from baseline in vital signs will be summarized for post-baseline assessment. The incidence of potentially clinical relevant vital signs, as defined in [Appendix 2](#) will be summarized by time point and mode of administration. Vital sign data that are potentially clinically relevant will also be listed out by subject.

When vital sign is repeated, the last repeat value will be used in the summary for that visit. Unscheduled vital sign data will not be summarized in the change from baseline table but will be included in incidence table.

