Appendix 3**Criteria for Identifying ECG Measurements of Potential Clinical Relevance**

Variable	Criterion Value ^a	Change Relative to Baseline ^a
Rhythm		
Sinus tachycardia ^b	≥ 110 bpm	increase of ≥ 15 bpm
Sinus bradycardia ^c	≤ 60 bpm	decrease of ≥ 15 bpm
Supraventricular premature beat	all	not present \rightarrow present
Ventricular premature beat	all	not present \rightarrow present
Supraventricular tachycardia	all	not present \rightarrow present
Ventricular tachycardia	all	not present \rightarrow present
Atrial fibrillation	all	not present \rightarrow present
Atrial flutter	all	not present \rightarrow present
Conduction		
1 atrioventricular block	$PR \geq 200$ msec	increase of ≥ 50 msec
2 atrioventricular block	all	not present \rightarrow present
3 atrioventricular block	all	not present \rightarrow present
Left bundle-branch block	all	not present \rightarrow present
Right bundle-branch block	all	not present \rightarrow present
Pre-excitation syndrome	all	not present \rightarrow present
Other intraventricular conduction block ^d	$QRS \geq 120$ msec	increase of ≥ 20 msec
Infarction		
Acute or subacute	all	not present \rightarrow present
Old	all	not present \rightarrow present
		≥ 12 weeks post trial entry
ST/T Morphological		
Myocardial ischemia	all	not present \rightarrow present
Symmetrical T-wave inversion	all	not present \rightarrow present
Increase in QTc		
< 12 years old	$QTcF \geq 450$ msec	increase of 60 msec
≥ 12 years old	$QTcF \geq 460$ msec	from baseline

QTc = corrected QT interval.

^aThe criterion value and change relative to baseline represented in this table are intended to identify on-treatment values outside of normal changes and that could potentially be clinically relevant. In order to be identified as potentially clinically relevant, the on-treatment value must meet the “Criterion Value” and also represent a change from the subject’s baseline value of at least the magnitude shown in the “Change Relative to Baseline” column. When evaluating these values, the emotional state of the subject must be taken into consideration (eg, crying, screaming) and documented as applicable.

^bNo current diagnosis of supraventricular tachycardia, ventricular tachycardia, atrial fibrillation, atrial flutter, or other rhythm abnormality.

^cNo current diagnosis of atrial fibrillation, atrial flutter, or other rhythm abnormality.

^dNo current diagnosis of left bundle branch block or right bundle branch block.

Protocol 405-201-00037

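### The SAP's relevance flag for heart rate and blood pressure does not require the change to be towards the limit crossed, so a value still beyond a limit but moving back towards normal can be counted

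*SAP*

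**What the plan says.** SAP Appendix 2 has two columns: a criterion value and a change relative to baseline. Footnote a requires both to be met, and describes the change only by its magnitude.

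- Heart rate: "< 60 bpm or > 110 bpm", with "Increase or decrease of ≥ 15 bpm".
- Systolic pressure, ages 6 to 9: "< 85 mmHg or > 115 mmHg", with "Increase or decrease of ≥ 20 mmHg".
- Systolic pressure, ages 10 to 12: "< 90 mmHg or > 120 mmHg", with a change of at least 15 mmHg either way.
- Diastolic pressure, ages 6 to 9: "< 50 mmHg or > 80 mmHg", with a change of at least 15 mmHg either way. At ages 10 to 12 the lower limit is 60 mmHg and the rest is the same.

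Protocol Appendix 6 (section 10.6) has the same rows. SAP section 10.4 uses the rule for a table ("The incidence of potentially clinical relevant vital signs, as defined in" Appendix 2), by time point and mode of administration, and for a by-subject listing. Baseline is the reading within 2 hours before dosing on Day 1.

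SAP Appendix 3 handles ECG heart rate differently. Tachycardia needs an "increase of ≥ 15 bpm" and bradycardia a decrease of the same size.

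**The concern.** The criteria are meant to pick out on-treatment values that are abnormal and have changed abnormally. Because each row puts both limits in one cell and both directions in the next, a high value that has fallen satisfies the rule as well as a high value that has risen. Reading the cells as "respectively" does not help: in the order printed, that would pair the low limit with an increase. No other text in either document supplies a direction.

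Protocol section 2.3 names increases in heart rate and blood pressure as a risk of the drug. A flag triggered by a fall from a raised predose reading, for instance in a child upset before dosing, would sit in the same table cell as a true rise. With at most 12 children, one such flag is visible in the percentages.

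**Working it through.** **No figure to reproduce.** The documents give no incidence or distribution for these flags. The check is of the rule's logic first, then of its likely frequency under stated assumptions.

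**1. The two rules.** Let b be baseline, v the on-treatment value, L and H the low and high limits, and d the magnitude.

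- As written: (v < L or v > H) and |v − b| ≥ d.
- Directional: (v > H and v − b ≥ d) or (v < L and b − v ≥ d).

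Over all integer pairs (b, v) from 20 to 200, every pair flagged by the directional rule is also flagged by the written rule. The written rule only adds pairs moving towards normal.

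**2. Where the extra flags begin.** In whole units, the lowest raised baseline that can be flagged on a fall is (H + 1) + d. The highest low baseline that can be flagged on a rise is (L − 1) − d.

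| Row | L, H, d | Flagged on a fall from | Flagged on a rise from |
|---|---|---|---|
| Heart rate (bpm) | 60, 110, 15 | 111 + 15 = 126 or more | 59 − 15 = 44 or less |
| Systolic, 6–9 (mmHg) | 85, 115, 20 | 116 + 20 = 136 or more | 84 − 20 = 64 or less |
| Systolic, 10–12 | 90, 120, 15 | 121 + 15 = 136 or more | 89 − 15 = 74 or less |
| Diastolic, 6–9 | 50, 80, 15 | 81 + 15 = 96 or more | 49 − 15 = 34 or less |
| Diastolic, 10–12 | 60, 80, 15 | 81 + 15 = 96 or more | 59 − 15 = 44 or less |

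**3. Examples.**

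- Flagged as written, not flagged by the directional rule: heart rate 128 → 112 (fall of 16, still above 110); systolic 137 → 121 at ages 10–12 (fall of 16, still above 120); diastolic 42 → 58 at ages 10–12 (rise of 16, still below 60).
- Flagged by neither: 120 → 112 (fall of only 8) and 130 → 105 (back inside the limits).
- Flagged by both: 95 → 111 (rise of 16).

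**4. Likely frequency for high heart rate.** Assumptions, none of them from the documents: normal readings, between-child SD 15, within-child SD 10, no drug effect, one pre/post pair per child. Then v has variance 15² + 10² = 325, v − b has variance 2 × 10² = 200, and their covariance is 10² = 100. The wrong-direction probability is p = P(v > 110 and b − v ≥ 15). The chance of at least one in 12 children is 1 − (1 − p)¹².

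| Mean (bpm) | p | Share of all high flags | At least one in 12 | No-drug readings above 110 |
|---|---|---|---|---|
| 85 | 0.23% | 7% | 1 − 0.9977¹² = 2.7% | 8% |
| 95 | 0.87% | 13% | 1 − 0.9913¹² = 10% | 20% |
| 105 | 2.45% | 21% | 1 − 0.9755¹² = 26% | 39% |

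The last column is P(v > 110) with SD √325 ≈ 18. Supine, standing and any further postdose readings would raise the per-child chance. They are correlated and are not modelled here.

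**5. Weight of one flag.** 1/12 = 8.3% overall, or 1/6 = 16.7% within a mode of administration if the split is even.

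**The case against.** **Reach.** A reader might infer that any child whose raised predose value settles will be counted. That does not follow. The value must still be beyond the limit and must have moved by the full magnitude; a child who returns inside the limits is not flagged. Protocol exclusion 15 removes children with diastolic pressure of 95 mmHg or more, which largely closes the high diastolic route (96 mmHg or more). The note to exclusion 14 lets the investigator exclude other medically significant vital signs, but there is no numeric bar for heart rate or systolic pressure, so a predose spike in either remains possible.

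**Frequency.** The 10–26% figures need means of 95–105 bpm, which would put 20–39% of untreated readings above 110. That is hard to square with a row labelled as resting heart rate, measured after at least 3 minutes in position (Protocol section 8.7.3). At 85 bpm the figure is about 3%. If the drug raised the mean by an assumed 5–10 bpm from 85, wrong-direction flags would be roughly 0.1–0.2% of pairs and 1–3% of high flags.

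**Comparison with the ECG table.** One might also infer that the same heart rate would be classified differently in two tables. The schedule does not support that. No ECG is planned at the 3-hour vital-sign time, and a Day 2 ECG is a separate reading with its own baseline. Appendix 3 shows how the rule can be worded; it does not show conflicting results.

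**Mitigation.** Footnote a asks that crying or screaming be considered and documented, SAP 10.4 lists flagged values by subject, and change from baseline is summarised separately. In a dozen children a falling value could be spotted. But the footnote gives no rule a programmer can apply to remove the flag, and the incidence table does not separate falls from rises.

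All of this bears on size. None of it makes the written rule directional.

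**Conclusion.** Wrong as written, minor. For heart rate, systolic and diastolic pressure, the Appendix 2 rule counts some values that are moving towards normal. This follows from the wording and needs no assumption. The frequency does rest on assumptions: about a 3% chance of one or more such high heart-rate flags in 12 children at a mean of 85 bpm, and higher only if the children's mean rate is well above that. No frequency was worked out for blood pressure.

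A reader might go further and infer that the safety conclusions or the trial's results are compromised. The documents do not support that. The fault only adds flags and misses no true worsening. It reaches a descriptive incidence table and a listing, while the primary endpoints are pharmacokinetic and there is no inferential or interim analysis.

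**What to change.** Add one clause to SAP Appendix 2, footnote a, for the section 10.4 incidence table: for heart rate, systolic and diastolic pressure, the change from baseline must be in the direction of the limit crossed, meaning an increase for the high limit and a decrease for the low limit. Leave every limit and magnitude as it stands.

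Reconcile Protocol Appendix 6 with the SAP wording. Protocol section 8.7.3 also uses that table to monitor subjects, so the sponsor should state whether the clause applies to monitoring or only to the SAP summary; this point takes no position on monitoring. Separate lines for high and low flags would help readers but are optional.

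The cost is one sentence and a small programming change, with no new data. Making it before the tables are programmed avoids deciding afterwards which flags count.
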